### **Methods**

Each subject will be evaluated at three visits following IOL implantation; visit 1 (1 month), Visit 2 (3-6 months) and visit 3 (12-18 months).

At each visit the following non-invasive visual function tests will be conducted: Monocular and binocular Unaided (UCVA) and Best Corrected Visual Acuity (BCVA) will be measured at 6 meters in LogMAR units using a calibrated computerised test chart.

Subjective and objective refraction will be used to determine if there is any residual refractive error.

Defocus curve profiles (visual acuity over imposed defocus) will be measured for each patient over a defocus range of +1.50D to -5.00D in 0.50D steps. The presentation of the letters and lenses will be randomised.

Contrast sensitivity will be evaluated monocularly under photopic and mesopic conditions using the Pelli-Robson Contrast Sensitivity Chart and CSV-1000.

Best distance corrected near and intermediate reading performance will be evaluated using the Radner Reading Charts and LogMAR charts and reading speed will be assessed in photopic conditions

Uncorrected and best distance corrected near acuity will be measured at 40cm

Uncorrected and best distance corrected intermediate acuity will be measured at 70cm.

The subject will be shown the Glare Simulator (Carl Zeiss Meditec) in order to assess the type of dysphotopsia present at each visit

A Halometer will be used to determine the size of the dysphotopsia

In order to assess the ocular biometry and record features of the IOL, at each visit the following imaging tests will be conducted following instillation of Tropicamide 1% to dilate the pupil:

- The Lenstar (Haagstreich) will be used to determine the post-operative axial position of the IOL following implantation.
- The A digital slit lamp camera will be used to image the IOL. This image will be used to determine if any decentration is present and if posterior capsular opacification is present using the EPCO 2000 software programme.

At each visit the following subjective assessment tests will be given to the patient to complete:

- The Visual satisfaction questionnaire will be used to determine the patient's overall satisfaction with their vision
- Near Assessment Visual Questionnaire (NAVQ) will be used to assess the patients satisfaction with their near and intermediate vision[14]

#### **Statistical Analysis:**

Normal distribution will be determined through examining histogram plots and with the Kolmogorov-Smirnov test. For analysis of the defocus curves the data will first be transformed into the defocus area metric[15] and the Radner reading chart data will also be converted according to the reading performance index.[16] Following this the means from each group will be assessed using two-way repeated measures ANOVA and a Pearson's coefficient will be used to look for correlations within the data. The results from the visual satisfaction questionnaire and NAVQ will be converted into Log RASCH units to provide a linear scale.

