## Introduction

With an ageing population, cataract surgery has become the most common surgical procedure carried out in the developed world. Approximately 2.5 million surgeries are preformed in the USA each year and approximately 250,000 are preformed in the UK.[1] Cataract surgery is also known as phacoemulsification and involves the extraction of the natural lens from its capsular bag and implantation of an artificial intraocular lens (IOL). The evolution of IOL designs has been rapid and extensive development of new advanced IOLs has occurred in recent years; spherical monofocal IOL designs are no longer the only pseudophakic option. Multifocal IOLs (MIOLs) are popular for the surgical correction of presbyopia because their mechanism of action is independent of ciliary body function. MIOLs provide high levels of spectacle independence[2] and currently are the most reliable lens for attaining both distance and near vision. This has lead to refractive lens exchange gaining popularity as increasing numbers of presbyopic patients look for refractive solutions. Monofocal intraocular lenses are the staple of cataract surgery providing excellent distance vision, however as patients expectations and demands rise, the need for correction of intermediate and near vision has become increasingly important. MIOLs restore some visual function at different distances by creating at least two focal points within the eye, corresponding to different working distances. Several mechanisms can be employed to create the simultaneous focal points and it is important to consider an MIOL's method of action as each lens has its own unique optical properties. The design of the MIOL affects the light distribution, the number of focal points, the distance of their separation, and ultimately the quality of the images. MIOLs can be divided into diffractive and refractive designs. Refractive designs can be subdivided into concentric and sectorial, while diffractive designs can be categorised as fully diffractive or partially diffractive.

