Intermediate visual function has posed a problem with MIOL implantation. A drop in acuity in the intermediate range has been reported with bifocal multifocal lenses. [3-5] Good intermediate vision is a requirement for certain individuals for occupational or recreational purposes and a sub-optimal acuity in the intermediate range can have a negative influence on the individual's quality of life[6] To this end recent MIOLs have been designed to improve intermediate vision by the use of a

lower add. These lenses provided good distance and near acuity as well as acceptable intermediate vision.[7-10]

With intermediate and near vision being essential in most individual's daily routine, it is clear that a solution is required and an IOL that can provide good vision at intermediate and near, without detriment to distance vision is needed. Visual acuity alone is not an adequate measure of success with MIOLs. All MIOLs create two or more simultaneous focal points within the eye. Therefore, at any one time at least one focal point will not be convergent on the retina. This defocused image causes a reduction in contrast and a distinctive photopic phenomenon known as Dysphotopsia.[2,12] This phenomenon, is one of the most common complaints with multifocal implantation and needs to be investigated to fully understand how the optical properties of an MIOL affect this photopic phenomenon.

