### **Aims:**

This study aims to evaluate the visual function and patient satisfaction of patients who have been implanted with the BiFlex M Multifocal IOL (Medicontur) and to compare the results with patients implanted with the BiFlex 1.8 monofocal IOL.

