#### **Sample Size**

Using GPower 3 a sample size of 50 subjects (100 eyes) per group was calculated for this study, therefore a total of 100 subjects will be recruited for the study.

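### No primary outcome, tested effect, significance level or multiplicity rule is named for well over a dozen outcomes, so the main lens result can be chosen after the data are seen

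*Combined protocol and SAP*

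**What the plan says.** The Aims section sets two broad domains: "This study aims to evaluate the visual function and patient satisfaction of patients" given the multifocal lens. It then intends "to compare the results with patients implanted with the BiFlex 1.8 monofocal IOL". No outcome is attached to that comparison.

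The Methods section schedules visits at 1 month, 3-6 months and 12-18 months. It introduces its test list with "At each visit the following non-invasive visual function tests will be conducted", and imaging and questionnaires are also repeated at every visit. Nothing in the list is ranked.

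The Statistical Analysis section covers normality checks, conversion of the defocus curves to an area metric, conversion of the Radner data to a reading index, Pearson correlations and Rasch scaling of the questionnaires. Its only group comparison is that "the means from each group will be assessed using two-way repeated measures ANOVA". The factors, the outcomes entered and the effect to be tested are not given.

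The Sample Size section says that "a sample size of 50 subjects (100 eyes) per group was calculated for this study" using GPower 3. It gives no endpoint, effect size, significance level or power.

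**The concern.** A randomised comparison needs one result fixed in advance as the answer. Here nothing separates the main lens result from the others. The sample-size paragraph, where a primary outcome can sometimes be inferred, does not point to one either.

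The choice matters because the lenses may differ in opposite directions. The Introduction says that multifocal lenses "currently are the most reliable lens for attaining both distance and near vision", and of the out-of-focus image it says: "This defocused image causes a reduction in contrast and a distinctive photopic phenomenon known as Dysphotopsia". A near-vision gain or a contrast loss could each be put forward as the headline once the data are known. With many outcomes and no error rule, a chance difference could also be reported as a finding.

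**Working it through.** **1. The plan's own figure.** The 50 per group cannot be reproduced, because no inputs are stated. It fits many input sets, for example a standardised difference of 0.566 at 80% power or 0.655 at 90% (two-sample t-test, two-sided 5%), or 0.5 one-sided at 80%. The sample size therefore does not identify an implied primary outcome.

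**2. Counting the outcomes in Methods.**

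| Outcome | Collapsed | Conditions counted apart |
|---|---|---|
| Distance acuity (unaided, corrected; monocular, binocular) | 2 | 4 |
| Refraction (subjective, objective) | 1 | 2 |
| Defocus area | 1 | 1 |
| Contrast (two charts; photopic, mesopic) | 2 | 4 |
| Reading (near, intermediate, speed) | 3 | 3 |
| Near acuity | 2 | 2 |
| Intermediate acuity | 2 | 2 |
| Dysphotopsia type and size | 2 | 2 |
| Axial position, decentration, capsular opacification | 3 | 3 |
| Questionnaires | 2 | 2 |
| **Total** | **20** | **25** |

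Leaving refraction out of the collapsed count gives 20 − 1 = 19. Leaving out the three imaging measures as well gives 16. At the other end, the wording of Statistical Analysis can be read as sending only about three derived scores (defocus area and the near and intermediate reading indices) into the ANOVA.

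**3. False-positive risk.** Assumptions, none of them from the documents: two-sided 5%, one lens test per outcome, all k outcomes null, and equal correlation r between test statistics. For independent tests the chance of at least one false lens difference is 1 − 0.95^k. For correlated tests it was computed from equicorrelated normal statistics.

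| k null outcomes | r = 0 | r = 0.5 | r = 0.8 |
|---|---|---|---|
| 3 | 14.3% | 12.5% | 9.8% |
| 16 | 56.0% | 37.4% | 20.7% |
| 19 | 62.3% | 40.9% | 22.0% |

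The narrow reading gives about 10% to 14% (r from 0.8 to 0). The wide reading gives about 21% to 41% (r from 0.8 to 0.5).

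**4. Choice of effect within one outcome.** If the factors are lens and visit (assumed), each outcome has two effects that involve lens: the main effect and the lens-by-visit interaction. Reporting whichever is significant gives 1 − 0.95² = 9.75% for a single null outcome.

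**5. What 50 per arm detects at 80% power, two-sided 5%.**
- One visit: 0.566 SD. With 10% lost (assumed; 45 per arm): 0.597 SD.
- Lens main effect over three visits: the SD of a patient's mean is √((1 + 2ρ)/3) times the single-visit SD, where ρ is the within-patient correlation. This assumes equal SDs and equal correlations across visits, a constant effect and complete data.
  - ρ = 0.5: 0.8165 × 0.566 = 0.46 SD
  - ρ = 0.6: 0.8563 × 0.566 = 0.485 SD
  - ρ = 0.8: 0.9309 × 0.566 = 0.53 SD
- A single-visit test has about 67% power for a difference of 0.485 SD.

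**6. Error control of the proposed rule.** With a primary at 5%, three secondaries under Holm and everything null, testing the secondaries regardless of the primary gives a family-wise error of 9.6%, 8.5% and 6.6% at r = 0, 0.5 and 0.8. Testing them only after a significant primary holds it at 5.0%.

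**The case against.** The strongest reply is that the aim is to evaluate and compare, with no stated hypothesis, so the study may be descriptive and need no formal error control. That would be a legitimate design, but the plan does not declare it. It specifies an ANOVA comparison of the groups and a calculated sample size. If the sponsor intends an exploratory study, it should say so and make no significance claims.

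A reader might also infer that outcomes will be tested separately at each of the three visits, which would multiply the tests. The documents do not support this. A repeated measures ANOVA can take all visits into one model, and visit-by-visit contrasts are not mentioned. The gap is the unnamed factors and effect.

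A reader might take 56% to 62% as the expected false-positive rate. That needs 16 to 19 outcomes that are all null and independent. Outcomes measured on the same patients are likely to be correlated, and the Introduction leads one to expect real differences on some of them. How many are null cannot be read from the documents, so no single row of the table is the plan's actual risk.

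Two further objections stand. Any exact outcome count depends on a counting rule, although every version is far above one. And moving to a single-visit test would cost power relative to the planned repeated-measures comparison, so it should not be imposed.

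**Conclusion.** The point holds. The plan names no primary outcome, effect of interest, significance level or multiplicity rule, and the sample-size paragraph does not supply them. This is more than missing detail: the plan as written lets the headline be selected after the data are seen and leaves the false-positive rate uncontrolled. Under the assumptions stated, the illustrative risk is about 10% to 14% on the narrowest reading and 21% to 41% with 16 to 19 correlated null outcomes.

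Two stronger conclusions a reader might draw are not supported. The documents show that the main result could be selected afterwards, not that it was or will be. Nor do they show that 50 per group is too few, because the difference it was meant to detect is not stated.

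The sponsor should correct this. The data would remain usable without the change, but no single lens difference could be presented as confirmatory.

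**What to change.** Before any outcome is compared by lens:

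1. Name one primary outcome, at the sponsor's choice, with one value per patient and the eye or binocular status stated.
2. Name one tested lens effect at two-sided 5%. This is either the lens main effect across the three visits in the planned ANOVA, with its factors stated, or the lens difference at one visit if the question concerns a particular time.
3. List a few fully specified key secondaries and test them by Holm only if the primary is significant.
4. Report all other outcomes and the Pearson correlations as estimates with 95% confidence intervals and no significance claim.
5. In Sample Size, state the endpoint, effect size, significance level and power entered in GPower. If these cannot be recovered, state what 50 per arm detects at 80% power for the chosen primary: about 0.57 SD at one visit (0.60 SD if 10% are lost), or about 0.46 to 0.53 SD for the three-visit lens effect, under the assumptions shown in the working.

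**Cost.** Plan wording only, with no new data or patients. Fewer outcomes can carry a significance claim. Secondaries depend on the primary: if a primary and a first secondary each have 80% power and are independent, both succeed in 0.80 × 0.80 = 64% of trials. With three secondaries, the first Holm step (0.05/3) needs about 0.66 SD at a single visit for 80% power with 50 per arm. Choosing one visit gives up some power against the three-visit effect.

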### **Exclusion Criteria:**

Amblyopia, post-op corneal astigmatism of  $\geq 1.50\text{D}$ , visual axis eccentricity of greater than 0.7mm, macular pathology, glaucoma, retinal disease, corneal disease, abnormal iris, pupil deformation and any previous corneal or intraocular surgery.

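### The two-way repeated measures ANOVA leaves its second factor and the handling of missed visits unstated; on the natural lens-by-visit reading it discards every patient with one missed visit

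*Combined protocol and SAP*

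**What the plan says.** The Statistical Analysis section first converts the defocus curves and the reading data to summary metrics. It then states that "the means from each group will be assessed using two-way repeated measures ANOVA". Its next step is exploratory: a Pearson "coefficient will be used to look for correlations within the data". It adds that "The results from the visual satisfaction questionnaire and NAVQ will be converted into Log RASCH units", but does not explicitly assign those scores a between-lens test.

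The Methods section schedules "visit 1 (1 month), Visit 2 (3-6 months) and visit 3 (12-18 months" after implantation, with the tests repeated each time. The questionnaires follow the same schedule: "At each visit the following subjective assessment tests will be given to the patient to complete". The same section also contains repeated conditions inside a single visit, for example "Contrast sensitivity will be evaluated monocularly under photopic and mesopic conditions".

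The Sample Size section gives 50 subjects per group, "therefore a total of 100 subjects will be recruited for the study". That is exactly 2 x 50, with no stated allowance for attrition. No section gives a dropout rate, a missing-data method or a missed-visit rule.

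**The concern.** The groups are the two lenses, so lens is one of the two factors. The other is left open. With three visits and every test repeated, visit is the natural candidate, although the plan does not say so.

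On that reading, the classical repeated measures ANOVA works on patients with all three visits. A patient seen at 1 month and at 3-6 months but not at 12-18 months contributes nothing to that outcome. Two things are then at stake:

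- **Precision.** Observed data are thrown away, so the standard error of the lens comparison grows.
- **Bias.** If patients with poorer results stay away more often, those left in an arm look better than the arm as a whole. The comparison shifts if this happens more strongly with one lens. It also shifts if the same rule acts in both arms and the lenses truly differ.

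Patient satisfaction is part of the stated aim and is collected at each visit, so attendance related to outcome is a reasonable risk to plan for.

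**Working it through.** **Inputs.** From the plan: 50 patients per group and three visits. Assumed, because the plan gives none of them: missed-visit rates, correlation r between visits of 0.5 or 0.7, SD 1 at each visit, higher score = better. The plan has no figure of its own to reproduce here: it states no effect size, SD, power or alpha.

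**1. Complete patients per group.**
- Misses independent across visits, 3/5/10%: 0.97 x 0.95 x 0.90 = 0.829, or 41.5 of 50. For 5/8/15%: 0.95 x 0.92 x 0.85 = 0.743, or 37.1.
- Misses nested (a patient once lost stays lost): 0.90, or 45; and 0.85, or 42.5.

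**2. Standard error of the visit-averaged lens difference, relative to full data.** For complete cases this is 1/√(complete fraction). With all available visits the variance is c′(Σ p_k Z_k′V_k⁻¹Z_k)⁻¹c. Here p_k is the share of patients with visit pattern k, Z_k selects the visits seen, V_k is their covariance and c = (1/3, 1/3, 1/3).

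| Missing at visits 1/2/3 | Pattern | Complete cases | All visits, r = 0.5 | All visits, r = 0.7 |
|---|---|---|---|---|
| 3/5/10% | independent | 1.098 | 1.011 | 1.006 |
| 3/5/10% | nested | 1.054 | 1.022 | 1.019 |
| 5/8/15% | independent | 1.160 | 1.018 | 1.010 |
| 5/8/15% | nested | 1.085 | 1.036 | 1.032 |

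If the second factor lies within a visit, only the missed visit is lost. The ratio is then 1/√(1 − m) for that visit, from 1.015 (m = 3%) to 1.085 (m = 15%).

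**3. Bias of the complete-case comparison.** Only visit 3 is missed, and dropout depends on the visit 2 result. If the completers' visit 2 mean lies k SD above that of their whole arm, the visit-averaged mean is shifted by k(1 + 2r)/3, that is 0.667k at r = 0.5 and 0.8k at r = 0.7. Bias is the difference in shift between arms, in favour of the arm that loses its poorer patients.

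- *Random loss, 20% v 5%:* k = 0 in both arms. Simulated bias is 0.00 SD.
- *Graded loss, 20% v 10%, same slope in both arms* (odds of dropout rising 2.0- to 2.7-fold per SD worse): k = 0.130 v 0.067 at the lower slope and 0.173 v 0.091 at the higher. Bias is 0.04-0.07 SD, with type I error about 6%.
- *Graded loss of 20% in the multifocal arm, random 10% in the other:* bias is 0.09-0.14 SD, with type I error 8-11%.
- *Threshold rule, multifocal arm only.* All patients more than 1 SD below the mean leave (16% v 0%): k = φ(1)/Φ(1) = 0.288, so bias is 0.192 (r = 0.5) or 0.230 (r = 0.7). Half of them leave (8% v 0%): k = 0.5φ(1)/(1 − 0.0793) = 0.131, so bias is 0.088 or 0.105. Type I error is 9-26% across these cases.
- *Same threshold in both arms, all leave, true difference −0.5 SD.* Losses are Φ(−0.5) = 31% v Φ(−1) = 16%. The shifts are φ(0.5)/Φ(0.5) = 0.509 v 0.288, a gap of 0.221, so bias is 0.148 or 0.177 SD. That is 30-35% of the true difference, and coverage of the 95% interval falls to as low as 82%. At −0.3 SD (24% v 16% lost) bias is 0.083 or 0.099 SD. With no true difference it is about 0.
- *As above, but only half leave, −0.5 SD* (15% v 8%): bias is 0.05-0.06 SD.

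**4. The likelihood alternative.** In simulation (8,000 trials per cell, 4,000 for both-arm cells with no true difference), a model with unstructured covariance using all observed visits had bias of at most 0.005 SD in every case above. Its type I error was 4.3-5.4% where there was no true difference. The exception is dropout that depends on the unseen visit 3 value. Under the threshold rule it is then biased too: 0.02-0.07 SD visit-averaged and 0.06-0.20 SD at visit 3, against 0.09-0.23 and 0.13-0.29 SD for complete cases.

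**The case against.** The strongest reply is that the discarding rests on a reading the plan does not state. The second factor could be lighting or another within-visit condition, and an analyst could fit a mixed model under the same label. This stands in part. On a within-visit reading the patient's other visits are kept, and the harm in steps 2 and 3 shrinks to the loss of the missed visit. The plan specifies neither that reading nor such a model, and on every reading the second factor and a missed-visit rule are absent.

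The sizes also need care. The largest both-arm figures need 31% v 16% lost, well above the 15% at the top of the range used for precision. Same-slope graded dropout moves type I error very little.

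A reader might infer more than the documents support:

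- *That neither factor is identified.* The reference to each group, with the Aims section, identifies lens.
- *That patients will be lost or the result biased.* No dropout rate is given, so neither follows.
- *That unequal dropout rates by themselves bias the comparison.* They do not when loss is unrelated to outcome (20% v 5% gave 0.00 SD).
- *That 50 per group is too few.* The inputs to that calculation are not stated, so this cannot be judged. No extra recruitment follows from this point.

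**Conclusion.** The concern holds, conditionally. The second factor and the missed-visit rule are missing on any reading. If the analysis is lens by visit with the classical ANOVA, the assumed losses leave 37 to 45 complete patients per group. The standard error then rises 5-16%, where 1-4% would suffice. Bias arises only if loss is related to outcome: about 0.04-0.14 SD for graded dropout at 20% v 10%. It reaches about 0.23 SD in the extreme case of 16% v 0%, and about 0.18 SD when one rule acts in both arms at a true difference of −0.5 SD.

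All of this rests on assumed dropout rates, mechanisms and correlations. With no primary outcome or effect size stated, the consequence for a particular conclusion cannot be judged. It is a cheap improvement worth making before results are seen. It is not evidence that the trial will mislead.

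**What to change.** In the Statistical Analysis section, replace only the ANOVA clause and keep the Pearson analysis:

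> For each outcome with one value per patient per visit, including the Rasch-scaled Visual satisfaction questionnaire and NAVQ scores, lens groups will be compared with a linear mixed model fitted by restricted maximum likelihood, with lens, visit and lens-by-visit as fixed effects and an unstructured within-patient covariance, using every available visit. The visit-averaged lens difference is the main contrast; differences at each visit are supportive. Missed visits will be reported by lens and visit.

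If a within-visit condition was the intended second factor, name it and add condition and lens-by-condition terms. Fitting each condition separately would lose the test of whether the lens difference varies by condition.

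The cost is one clause and slightly more analysis work in standard software, with no extra patients or visits. The downside is reliance on data being missing at random given the observed visits. That is weaker than what the complete-case ANOVA needs, but it cannot be tested from the data. The clause does not cover outcomes measured in each eye; how to model those is a separate point.
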